15.2 Visual Acuity (VA)

The VA procedure will be performed at each scheduled visit. The logarithm of the minimum angle of resolution (logMAR) VA must be assessed using an Early Treatment of Diabetic Retinopathy Study (ETDRS) chart. The procedure used will be consistent with the recommendations provided for using the ETDRS eye chart. Visual Acuity should be evaluated at the beginning of each visit in the study (i.e., prior to slit-lamp examination). Subjects should use their most recent correction to attain their best-corrected visual acuity (BCVA).

The observed VA and change from baseline in VA will be summarized for each eye (study eye and fellow eye) using continuous descriptive statistics by visit for each treatment group. The number and percentage of subjects who had logMAR change from baseline $\geq +0.22$ will be summarized for each eye by treatment group. The worst on-treatment value also will be summarized, and the CFB for the worst on-treatment value will be summarized analogously.

A subject listing of VA will also be produced.

15.3 Slit-Lamp Biomicroscopy Examination

A slit-lamp biomicroscopy examination of the cornea, conjunctiva, anterior chamber, iris, lens, and eyelid will be performed at each visit. The results will be graded as Normal, Abnormal Not Clinically Significant (NCS), or Abnormal Clinically Significant (CS). Abnormal findings will be described.

The results will be summarized using counts and percentages for each treatment group at each visit for each eye (study eye and fellow eye). Percentages will be based on the number of subjects in each treatment group with responses. Shift tables for the slit-lamp biomicroscopy parameters will also be provided comparing each follow-up visit to baseline. The worst on-treatment value and the shift from baseline for the worst on-treatment value also will be summarized.

A subject listing of the slit-lamp biomicroscopy parameters will also be produced.

15.4 Dilated Fundoscopy Examination

A dilated fundoscopy exam will be performed during the study at Day -14 and Day 57, and potentially at unscheduled visit assessments. Observations of the vitreous, retina, macula, choroid, and optic nerve will be graded as Normal, Abnormal NCS, or Abnormal CS. Abnormal findings will be described.

The results will be summarized using counts and percentages for each treatment group at each visit for each eye (study eye and fellow eye). Percentages will be based on the number of subjects in each treatment group with responses. Shift tables for the dilated fundoscopy parameters will also be provided comparing Day 57 to baseline. The worst on-treatment value and the shift from baseline for the worst on-treatment value also will be summarized.

A subject listing of the dilated fundoscopy parameters will also be produced.

15.5 Intraocular Pressure (IOP)

Intraocular pressure will be measured in each eye by contact tonometry by the examiner and the results will be recorded in mmHg at Day -14 and Day 57. A single measurement is made to obtain a determination of IOP. The same tonometer employing the investigator's standard technique will be used throughout the study. In addition, all reasonable efforts will be made to have the same examiner obtain all IOP measurements for a given subject.

The IOP values and changes from baseline for each eye (study eye and fellow eye) will be summarized using continuous descriptive statistics by visit and eye for each treatment group. The worst on-treatment value also will be summarized, and the CFB for the worst on-treatment value will be summarized analogously.

A subject listing of IOP will also be produced.

15.6 Immunogenicity to Tanfatercept Ophthalmic Solution 0.25% in Serum

Serum blood draws will be collected at Day 1, Day 29, and Day 57 for immunogenicity testing. Instructions for the collection, handling, and shipping of blood for immunogenicity testing are given in a separate laboratory manual. Analyses of immunogenicity data will be conducted as ad-hoc analyses. The anticipated ad-hoc analyses of immunogenicity are as follows.

Immunogenicity will be summarized using discrete summary statistics. Counts and proportions of subjects with anti-drug antibodies (ADA) will be presented by visit and treatment group. Exact 95% Clopper-Pearson CIs will be presented. Treatment groups will be compared using Fisher's exact test, and exact 95% confidence intervals for the pairwise proportion differences will be constructed.

Antibody titer of subjects positive for ADA will be summarized using continuous descriptive statistics and presented by visit and treatment group. Treatment groups will be compared using two-sample t-tests. The differences in means, two-sided 95% CIs for the difference in means, and p-values will be reported.

16. Other Endpoints

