6.2 Safety Measures

- Visual acuity
- Slit-lamp evaluation
- Adverse event query
- Intraocular Pressure (IOP)
- Dilated fundoscopy
- Immunogenicity to tanfanercept in serum

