8.4 Examination Procedures

An ICF must be signed and dated by the subject, the principal investigator (PI) or designee and witness (if required) before any study-related procedures are performed.

Procedures listed below should be performed in the given order. See [Appendix 3](#): Examination Procedures, Tests, Equipment, and Techniques for details on methodologies and grading systems.

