- Note: If only one eye qualifies then the single qualifying eye will be the study eye. In the case that both eyes are eligible for analysis, the study eye will be the eye with worse (higher) central corneal fluorescein staining at Visit 2. If the central corneal fluorescein staining is the equivalent in both eyes, then the right eye will be selected as the study eye.
- **Randomization** – subjects will be randomized according to the following two strata:
 1. Visit 2 study eye CCSS █ and
 2. Visit 1 CCSS minus Visit 2 CCSS (V1 CCSS - V2 CCSS); difference in study eye CCSS █
- **Blood Sampling** Blood samples will be collected from all subjects for immunogenicity testing █

- Study Drug Instillation at the Study Site All subjects meeting all other screening eligibility criteria after Visit 2 will be randomized to one of two treatment arms. Randomized subjects will self-administer their initial study drug dose bilaterally at the study site.
- Ora Calibra® Drop Comfort Assessments The Ora Calibra® Drop Comfort Scale will be performed immediately after instillation and then at 1, 2, and 3 minutes following instillation.
- Monitoring and Query of AEs
- Study Drug Dispensation Prior to discharge from the study site on Visit 2 (Day 1), randomized subjects will be educated in the self-administration of study drug. The initial, self-administered dose taken in-office at Visit 2 will be counted as a morning dose regardless of visit time, and subjects will be instructed to administer an evening dose that night. Subjects will receive their assigned study drug kit with sufficient supply to last until Visit 3 and will be instructed NOT to self-administer study drug on the morning of their next scheduled study visit (Visit 3, Day 8).
- Schedule Next Visit Subjects will be scheduled for Visit 3.

8.4.4 Visit 3: Day 8 ± 1 –Week 1

- Study Drug Collection All used/unused study drug vials dispensed for Days 1 to 8 should be collected and reviewed by a trained study technician.
- Site staff must confirm that subjects have NOT administered their morning study drug dose at home. If subject dosed prior to the visit, study visit procedures should begin 4 hours after time of dosing.
- Monitoring and Query AEs
- Recording of all Changes in Concomitant Medications
- Ora Calibra® Ocular Discomfort Scale
- Ora Calibra® Ocular Discomfort & 4-Symptom Questionnaire
- VAS
- OSDI[©]
- BCVA Utilizing an ETDRS Chart
- Slit-Lamp Biomicroscopy
- Conjunctival Redness
- TFBUT

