[REDACTED]  
LSMEANS TREATMENT / CL PDIFF;  
RUN;
```

25. Appendix 2

Schedule of Visits and Assessments

Procedure	Screening Visit 1 (Day -14 ± 2)	Baseline Visit 2 (Day 1)	Visit 3 (Day 8 ± 1)	Visit 4 (Day 15 ± 2)	Visit 5 (Day 29 ± 2)	Visit 6 (Day 57 ± 3)	Visit 7-9 ⁴
Informed Consent / HIPAA	X						
Medical / Medication History and Demographics	X						
Placebo Run-In Collection		X					
Study Drug Collection			X	X	X	X	
Medical / Medication Update		X	X	X	X	X	X
Pregnancy Test	X ²					X ²	
Ocular Discomfort Scale	X	X	X	X	X	X	
Ocular Discomfort & 4-Symptom Questionnaire	X	X	X	X	X	X	
VAS	X	X	X	X	X	X	
OSDI® Questionnaire	X	X	X	X	X	X	
Visual Acuity (ETDRS)	X	X	X	X	X	X	
Slit Lamp Biomicroscopy	X	X	X	X	X	X	
Conjunctival Redness	X	X	X	X	X	X	
TFBUT	X	X	X	X	X	X	
Fluorescein Stainng	X	X	X	X	X	X	
Lissamine Green Staining	X	X	X	X	X	X	
Schirmer's Test	X	X		X	X	X	
Intraocular Pressure	X					X	
Dilated Fundus Exam	X					X	
Review of Qualification Criteria	X	X					

Placebo Run-In Dispensation and Instillation	X						
Blood Sampling for Immunogenicity		X			X	X	X
Randomization		X					
Study Drug Instillation		X	X				
Drop Comfort Scale		X	X				
Drop Comfort Questionnaire		X	X				
Adverse Event Query	X	X	X	X	X	X	X
Study Drug Dispensation		X ¹	X	X	X		
Exit Subject from Study						X ³	

¹ The Visit 2 study drug kit is re-dispensed at Visit 3 (as each kit includes 2-week supply of study drug).

² To women of child-bearing potential.

³ For subjects with negative immunogenicity results at Visit 6.

⁴ Subjects will be asked to return for Blood Sample for Immunogenicity Testing if they test positive for immunogenicity at Visit 6. Visit 7 will occur approximately 6-12 months after Visit 6. If subject tests positive for immunogenicity at Visit 7, they will be asked to return for Visit 8 approximately 12 months after Visit 7. If subject tests positive for immunogenicity at Visit 8, subject will be asked to return for Visit 9 approximately 12 months after Visit 8.

Certificate Of Completion

Envelope Id: 0FD96C8D49AC44D78A4A23EF3B2091D1 Status: Completed

Subject: Complete with DocuSign: HanAll HL036-DED-US-P302 Statistical Analysis Plan Draft V1.0 23-JAN-20...

Source Envelope:

[figure not shown]
Document Pages: 45 Signatures: 3

Certificate Pages: 5 Initials: 0

AutoNav: Enabled

Enveloped Stamping: Disabled

Time Zone: (UTC-05:00) Eastern Time (US & Canada)

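### SAP 15.6 analyses antibody positivity visit by visit and never links it to the pre-dose Day 1 sample, so active-arm rates and titres mix pre-existing with treatment-induced antibody and the between-arm test loses power

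*SAP*

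**What the plan says.** Protocol section 6.2 lists "Immunogenicity to tanfanercept in serum" among the safety measures. SAP section 15.6 sets the sampling times: "Serum blood draws will be collected at Day 1, Day 29, and Day 57 for immunogenicity testing".

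The Day 1 draw comes before dosing. Protocol section 8.4 says "Procedures listed below should be performed in the given order", and the Visit 2 list in section 8.4.3 puts blood sampling ("Blood samples will be collected from all subjects for immunogenicity testing") ahead of the first instillation of randomised drug.

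SAP section 15.6 labels its immunogenicity analyses as anticipated and ad hoc, but writes them out:

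- **Positivity:** "Counts and proportions of subjects with anti-drug antibodies (ADA) will be presented by visit and treatment group", with Clopper-Pearson intervals.
- **Between-arm test:** "Treatment groups will be compared using Fisher's exact test, and exact 95% confidence intervals for the pairwise proportion differences will be constructed".
- **Titre:** "Antibody titer of subjects positive for ADA will be summarized using continuous descriptive statistics and presented by visit and treatment group", with two-sample t-tests between arms.

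Neither document defines treatment-induced or treatment-boosted antibody, a change from Day 1 in status or titre, or a split by Day 1 status. The SAP table list (section 21) has no immunogenicity table. The listings (section 22) have only one for the blood draw.

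**The concern.** The quantity of interest is antibody raised by the drug. A by-visit count treats a subject who was already reactive before dosing exactly like one who seroconverts on treatment. Three results are affected.

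1. **The active-arm proportion and its interval.** Readers will take this as the drug's antibody rate. It includes pre-existing reactivity, and the placebo arm does not correct a figure reported within one arm.
2. **The titre comparison.** It is restricted to antibody-positive subjects, a group formed after randomisation. On active these are pre-existing plus induced positives; on placebo they are mainly pre-existing. Many new low titres on active could pull that arm's mean down and mask rising titres in subjects who were positive on Day 1.
3. **The Fisher test.** Background positives in both arms add noise to a comparison that may involve few events.

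The SAP relates other safety measures to baseline: change from baseline for visual acuity and intraocular pressure (15.2, 15.5), and shift tables for slit lamp and fundoscopy (15.3, 15.4). Immunogenicity has a pre-dose sample but gets neither.

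**Working it through.** The documents state no antibody rate, power or sample size for immunogenicity, so there is no plan figure to reproduce.

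**Inputs from the documents.** 130 randomised per arm (SAP section 5); two-sided 0.05 (SAP 8.4); Fisher's exact test (SAP 15.6).

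**Assumptions.**
- p0, the share positive on Day 1: 0% to 10%, the same in both arms and persisting to Day 57.
- d, the share of Day 1 negatives on active who turn positive because of the drug: 8%.
- New positives on placebo: none at first, then 2%.
- Every subject has a result. Boosting is left out of the calculation.

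**Formulas.**
- All positives: active p0 + (1 − p0)d; placebo p0.
- New positives only, over the whole arm: active (1 − p0)d; placebo 0.
- Risk difference: (1 − p0)d under both definitions.
- Share of active positives that pre-date dosing: p0 / [p0 + (1 − p0)d].
- Power: the sum of the two-binomial probabilities over all tables with Fisher p ≤ 0.05.

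Example at p0 = 5%: active 0.05 + 0.95 × 0.08 = 12.6% and placebo 5.0%, a difference of 7.6 points. New positives are 0.95 × 0.08 = 7.6% against 0%, again 7.6 points. The pre-existing share is 5.0 / 12.6 = 40%.

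| p0 | Active v placebo, all positives | New positives | Pre-existing share of active positives | Power, all positives | Power, new positives |
|---|---|---|---|---|---|
| 0% | 8.0% v 0% | 8.0% v 0% | 0% | 95% | 95% |
| 3% | 10.8% v 3.0% | 7.8% v 0% | 28% | 62% | 94% |
| 5% | 12.6% v 5.0% | 7.6% v 0% | 40% | 50% | 94% |
| 10% | 17.2% v 10.0% | 7.2% v 0% | 58% | 33% | 91% |

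With 117 per arm (130 × 0.9) and p0 = 5%, power is 44% v 89%.

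**Background positives.** Suppose 2% of Day 1 negatives in both arms turn positive for reasons unrelated to the drug. The active conversion rate becomes 1 − 0.92 × 0.98 = 9.84%. At p0 = 5%:
- All positives: 0.05 + 0.95 × 0.0984 = 14.3% v 0.05 + 0.95 × 0.02 = 6.9%. Power 42%.
- New positives: 9.3% v 1.9%. Power 68%.

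At p0 = 1% the same calculation gives 63% v 70%.

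**Validity.** With no induction, the Fisher test on all positives rejects 2.2% of the time at p0 = 5% and 3.0% at p0 = 10%, both under 5%. The standard deviation of the chance Day 1 difference between arms is √(2 × 0.05 × 0.95 / 130) = 2.7 points at p0 = 5%. By-visit prevalence carries that noise through to Day 57.

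**The case against.** The strongest reply is that the trial is randomised 1:1 against placebo. Pre-existing antibody is balanced in expectation, so the Day 57 difference estimates drug-induced antibody under either definition. That stands. A reader might infer that the planned comparison fails to measure immunogenicity to tanfanercept; the equal risk differences and the controlled type I error show that it does measure it, with less precision.

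Other stronger readings also fail:

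- **That Day 1 is unused.** The by-visit presentation includes Day 1, so baseline prevalence by arm will be visible. What is missing is the link within each subject.
- **That a rising titre in a Day 1 positive goes uncounted.** It enters the by-visit titre summary, though only as part of a mean among positives.
- **That Fisher's test is the only formal look.** The titre t-test is another.
- **That the recall rule in SAP Appendix 2, footnote 4, shares the fault** ("Subjects will be asked to return for Blood Sample for Immunogenicity Testing if they test positive for immunogenicity at Visit 6"). It governs subject follow-up and is not an estimator. No harm from it is shown, and the visible protocol text around blood sampling is partly redacted.

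The reply also notes that the analyses are labelled ad hoc, that no immunogenicity test is powered, and that SAP section 1 allows additional analyses. This limits the severity. But since the SAP writes the method out, the definition belongs with it, fixed before unmasking.

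Finally, the power gain depends on assumed rates. Protocol section 5.4 excludes prior users of TNF-inhibitor eye drops, and pre-existing reactivity may be low. At zero the two definitions coincide, and background conversion on placebo shrinks the gain. Both limits are accepted and shown in the working.

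**Conclusion.** The point holds in limited form. SAP 15.6 does not separate pre-existing from treatment-induced antibody, although the sample needed to do so is collected. The within-arm rate and the titre comparison are the results most affected, because randomisation protects neither. At 5% pre-existing and 8% induction, 40% of active-arm positives would pre-date dosing. Boosting can be seen only through a mean titre in a subset formed after randomisation.

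The between-arm Fisher comparison remains valid but is diluted. Under the assumed rates the loss runs from nothing at 0% pre-existing to 33% against 91% power at 10%. It is 42% against 68% at 5% pre-existing when 2% of Day 1 negatives in each arm convert for other reasons. All of these rates are assumptions. The existence of the gap does not depend on them; its size does.

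**What to change.** In SAP section 15.6:

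1. Define treatment-induced antibody as negative on Day 1 and positive at any later sample.
2. Define treatment-boosted antibody as positive on Day 1 with a later titre at least a pre-specified fold above Day 1, the fold being taken from the assay validation.
3. Apply the proportion, Clopper-Pearson interval and Fisher test to treatment-emergent antibody (induced or boosted) by Day 57, and state the denominator.
4. Add a shift table of Day 1 against post-baseline status by arm.
5. Keep by-visit prevalence as a descriptive table.

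Leave the Visit 7-9 recall trigger as it is.

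The cost is SAP wording, one derived variable and one table, with no new samples. The small downside is that Day 1 positives without a qualifying titre rise leave the numerator; they remain visible in the shift and prevalence tables.

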16.1 Ora Calibra® Drop Comfort Scale and Questionnaire

16.1.1 ORA CALIBRA® DROP COMFORT SCALE

Drop comfort will be assessed for each eye immediately upon instillation, and at 1 and 2 minutes following initial dosing at Day 1 and Day 8 using the Ora Calibra® Drop Comfort Scale. [REDACTED]

[REDACTED] Drop comfort will be summarized by visit and time point using quantitative summary statistics. Two-sample t-tests will be employed to compare the actual scores of the active treatment and placebo. The differences in means, SEs, two-sided 95% CIs for the difference in means, and p-values will be reported. Analyses will be performed on the ITT population with observed data only for the study eye.

16.1.2 ORA CALIBRA® DROP COMFORT QUESTIONNAIRE

Descriptions of drop comfort will be assessed at 3 minutes following initial dosing at Day 1 and Visit 3 (Day 8) using the Ora Calibra® Drop Comfort Questionnaire. On this questionnaire, subjects will be asked to choose three words that best describe how each eye drop feels in both of his/her eyes. [REDACTED]

[REDACTED] Subjects may also select "other" and write in a response of their choosing, which may be either a positive or a negative response. Drop Comfort Questionnaire responses will be summarized by treatment group using qualitative summary statistics. Subjects with at least one negative response as well as subjects with at least one positive response will also be summarized by treatment group. Analyses will be performed on the ITT population with observed data only.

17. Interim Analyses

No interim analyses are planned for this study.

18. Changes from Protocol-Stated Analyses

There are no changes from the protocol-stated analyses.

19. References

20. Revision History

Revision history will be documented for any change in the organization responsible for SAP authorship and after the final execution of Version 1.0 of this SAP.

21. Tables

Ten tables that will be included in the topline delivery are shown in boldface font.

^{1,2} One of the two sets of primary endpoint tables will be delivered with topline according primary estimand defined in [section 2.6](#).

Table Number	Title	Population
Table 14.1.1	Subject Disposition	All Randomized Subjects
Table 14.1.2.1	Demographics	ITT Population
Table 14.1.2.2	Demographics	Safety Population
Table 14.1.3.1	Baseline Disease Characteristics (Study Eye)	ITT Population
Table 14.1.4.1	Ocular Medical History	ITT Population
Table 14.1.4.2	Non-Ocular Medical History	ITT Population
Table 14.1.5.1	Ocular Concomitant Medications by Treatment Group, Drug Class, and Preferred Name	ITT Population
Table 14.1.5.2	Non-Ocular Concomitant Medications by Treatment Group, Drug Class, and Preferred Name	ITT Population
Table 14.1.6.1	Ocular Concomitant Procedures	ITT Population
Table 14.1.6.2	Non-Ocular Concomitant Procedures	ITT Population
Table 14.1.7	Subject Pooling by Site	All Randomized Subjects
Table 14.2.1.1	Central Corneal Fluorescein Staining (Ora Calibra Scale) at Visit 6 (Day 57)	ITT Population with Multiple Imputation

Table Number	Title	Population
		Methodology (Estimand 1) ¹
Table 14.2.1.2	Central Corneal Fluorescein Staining (Ora Calibra Scale) at Visit 6 (Day 57): Permutation Test with Trimmed Means	ITT Population with Single Imputation Methodology (Estimand 2) ¹
Table 14.2.1.3	Central Corneal Fluorescein Staining (Ora Calibra Scale) at Visit 6 (Day 57)	ITT Population with PMM
Table 14.2.1.4	Central Corneal Fluorescein Staining (Ora Calibra Scale) at Visit 6 (Day 57)	ITT Population with MCMC
Table 14.2.1.5	Central Corneal Fluorescein Staining (Ora Calibra Scale) at Visit 6 (Day 57)	ITT Population with LOCF
Table 14.2.1.6	Central Corneal Fluorescein Staining (Ora Calibra Scale) at Visit 6 (Day 57)	ITT Population with Observed Data Only
Table 14.2.1.7	Central Corneal Fluorescein Staining (Ora Calibra Scale) at Visit 6 (Day 57)	PP Population with Observed Data Only
Table 14.2.1.1.1	Central Corneal Staining Score (Ora Calibra Scale) at Visit 6 (Day 57) – Site Analysis	ITT Population with Multiple Imputation (Estimand 1)
Table 14.2.2.1	Eye Dryness Score (Visual Analog Scale) at Visit 6 (Day 57)	ITT Population with Multiple Imputation Methodology (Estimand 1) ²
Table 14.2.2.2	Eye Dryness Score (Visual Analog Scale) at Visit 6 (Day 57): Permutation Test with Trimmed Means	ITT Population with Single Imputation Methodology (Estimand 2) ²
Table 14.2.2.2	Eye Dryness Score (Visual Analog Scale) at Visit 6 (Day 57)	ITT Population with PMM
Table 14.2.2.3	Eye Dryness Score (Visual Analog Scale) at Visit 6 (Day 57)	ITT Population with MCMC
Table 14.2.2.4	Eye Dryness Score (Visual Analog Scale) at Visit 6 (Day 57)	ITT Population with LOCF

Table Number	Title	Population
Table 14.2.2.5	Eye Dryness Score (Visual Analog Scale) at Visit 6 (Day 57)	ITT Population with Observed Data Only
Table 14.2.2.6	Eye Dryness Score (Visual Analog Scale) at Visit 6 (Day 57)	PP Population with Observed Data Only
Table 14.2.2.1.1	Eye Dryness Score (Visual Analog Scale) at Visit 6 (Day 57) – Site Analysis	ITT Population with Multiple Imputation Methodology (Estimand 1)
Table 14.2.3	Fluorescein Corneal and Conjunctival Staining (Ora Calibra Scale)	ITT Population with Observed Data Only
Table 14.2.4	Lissamine Green Corneal and Conjunctival Staining (Ora Calibra Scale)	ITT Population with Observed Data Only
Table 14.2.5	Conjunctival Redness Scale (Ora Calibra Scale)	ITT Population with Observed Data Only
Table 14.2.6	Unanesthetized Schirmer's Test (mm)	ITT Population with Observed Data Only
Table 14.2.7	Tear Film Break-Up Time	ITT Population with Observed Data Only
Table 14.2.8	Visual Analog Scale	ITT Population with Observed Data Only
Table 14.2.9	Ocular Surface Disease Index (OSDI)	ITT Population with Observed Data Only
Table 14.2.10	Ocular Discomfort Scale (Ora Calibra Scale)	ITT Population with Observed Data Only
Table 14.2.11	Ocular Discomfort & 4-Symptom Questionnaire (Ora Calibra Scale)	ITT Population with Observed Data Only
Table 14.2.12	Summary of Efficacy Analyses	Multiple Populations
Table 14.3.1.1	Overall Adverse Event Summary	Safety Population
Table 14.3.1.2	All Conjunctivitis Adverse Events	Safety Population

Table Number	Title	Population
Table 14.3.1.3	All Ocular Adverse Events	Safety Population
Table 14.3.1.4	All Non-Ocular Adverse Events	Safety Population
Table 14.3.1.5	All Ocular Treatment-Emergent Adverse Events	Safety Population
Table 14.3.1.6	All Non-Ocular Treatment-Emergent Adverse Events	Safety Population
Table 14.3.1.7	All Ocular Treatment-Related Treatment-Emergent Adverse Events	Safety Population
Table 14.3.1.8	All Non-Ocular Treatment-Related Treatment-Emergent Adverse Events	Safety Population
Table 14.3.1.9	All Serious Adverse Events	Safety Population
Table 14.3.1.10	All Ocular Treatment-Emergent Adverse Events by Maximal Severity	Safety Population
Table 14.3.1.11	All Non-Ocular Treatment-Emergent Adverse Events by Maximal Severity	Safety Population
Table 14.3.1.12	All Ocular Treatment-Emergent Adverse Events by Study Day of Onset	Safety Population
Table 14.3.1.13	All Non-Ocular Treatment-Emergent Adverse Events by Study Day of Onset	Safety Population
Table 14.3.2	Visual Acuity (logMAR)	Safety Population
Table 14.3.3.1	Slit Lamp Biomicroscopy	Safety Population
Table 14.3.3.2	Shift in Slit Lamp Biomicroscopy	Safety Population
Table 14.3.4.1	Dilated Fundoscopy	Safety Population
Table 14.3.4.2	Shift in Dilated Fundoscopy	Safety Population
Table 14.3.5	Intraocular Pressure (mmHg)	Safety Population
Table 14.3.6.1	Ora Calibra Drop Comfort Scale	ITT Population with Observed Data Only

Table Number	Title	Population
Table 14.3.6.2	Ora Calibra Drop Comfort Questionnaire	ITT Population with Observed Data Only
Table 14.3.7	Compliance with Study Drug	Safety Population
Table 14.3.8	Exposure to Study Drug	Safety Population

22. Listings

Listing Number	Title	
Listing 16.1.7	Randomization Schedule	All Randomized Subjects
Listing 16.2.1	Subject Disposition	All Randomized Subjects
Listing 16.2.2	Protocol Deviations	All Screened Subjects
Listing 16.2.3.1	Study Population Inclusion	All Randomized Subjects
Listing 16.2.3.2	Inclusion/Exclusion and Screen Failures	All Screened Subjects
Listing 16.2.3.3	Subjects Affect By COVID-19	All Randomized Subjects
Listing 16.2.4.1	Demographics	All Screened Subjects
Listing 16.2.4.2	Ocular Medical History	All Randomized Subjects
Listing 16.2.4.3	Non-Ocular Medical History	All Randomized Subjects
Listing 16.2.4.4	Prior and Concomitant Ocular Medications	All Randomized Subjects

Listing Number	Title	
Listing 16.2.4.5	Prior and Concomitant Non-Ocular Medications	All Randomized Subjects
Listing 16.2.4.6	Ocular Concomitant Procedures	All Randomized Subjects
Listing 16.2.4.7	Non-Ocular Concomitant Procedures	All Randomized Subjects
Listing 16.2.5.1	In-Office Run-In and Study Drug Instillation	All Randomized Subjects
Listing 16.2.5.2	Run-In Kit Assignment and Replacement	All Randomized Subjects
Listing 16.2.5.3	Study Drug Kit Assignment and Replacement	All Randomized Subjects
Listing 16.2.5.4	Study Drug Accountability	All Randomized Subjects
Listing 16.2.5.5	Study Drug Exposure and Dosing Compliance	All Randomized Subjects
Listing 16.2.6.1	Fluorescein Corneal and Conjunctival Staining (Ora Calibra Scale)	All Randomized Subjects
Listing 16.2.6.2	Lissamine Green Corneal and Conjunctival Staining (Ora Calibra Scale)	All Randomized Subjects
Listing 16.2.6.3	Conjunctival Redness (Ora Calibra Scale)	All Randomized Subjects
Listing 16.2.6.4	Unanesthetized Schirmer's Test	All Randomized Subjects
Listing 16.2.6.5	Tear Film Break Up Time (TFBUT)	All Randomized Subjects
Listing 16.2.6.6	Visual Analog Scale	All Randomized Subjects

Listing Number	Title	
Listing 16.2.6.7	Ocular Surface Disease Index (OSDI)	All Randomized Subjects
Listing 16.2.6.8	Ocular Discomfort Scale (Ora Calibra Scale)	All Randomized Subjects
Listing 16.2.6.9	Ocular Discomfort & 4-Symptom Questionnaire (Ora Calibra Scale)	All Randomized Subjects
Listing 16.2.6.10	Ora Calibra Drop Comfort Scale	All Randomized Subjects
Listing 16.2.6.11	Ora Calibra Drop Comfort Questionnaire	All Randomized Subjects
Listing 16.2.7.1	All Adverse Events	All Randomized Subjects
Listing 16.2.7.2	Serious Adverse Events	All Screened Subjects
Listing 16.2.7.3	Adverse Events Leading to Treatment Discontinuation	All Randomized Subjects
Listing 16.2.7.4	Adverse Events Leading to Death	All Randomized Subjects
Listing 16.2.7.5	Conjunctivitis Adverse Events	All Randomized Subjects
Listing 16.2.8.1	Visual Acuity (logMAR)	All Randomized Subjects
Listing 16.2.8.2	Slit Lamp Biomicroscopy	All Randomized Subjects
Listing 16.2.8.3	Dilated Fundoscopy	All Randomized Subjects
Listing 16.2.8.4	Intraocular Pressure (IOP)	All Randomized Subjects

Listing Number	Title	
Listing 16.2.8.5	Blood Draw for Immunogenicity	All Randomized Subjects
Listing 16.2.8.6	Urine Pregnancy Test	All Randomized Subjects

23. Figures

Figure Number	Title	Population
Figure 14.2.1.1	Change from Baseline of Central Corneal Fluorescein Staining (Ora Calibra Scale) at Visit 6 (Day 57)	ITT Population with Multiple Imputation Methodology (Estimand 1)
Figure 14.2.2.1	Change from Baseline of Eye Dryness Score (Visual Analog Scale) at Visit 6 (Day 57)	ITT Population with Multiple Imputation Methodology (Estimand 1)
Figure 14.2.3	Fluorescein Corneal and Conjunctival Staining (Ora Calibra Scale)	ITT Population with Observed Data Only
Figure 14.2.4	Lissamine Green Corneal and Conjunctival Staining (Ora Calibra Scale)	ITT Population with Observed Data Only
Figure 14.2.5	Unanesthetized Schirmer's Test	ITT Population with

Figure Number	Title	Population
		Observed Data Only
Figure 14.2.6	Visual Analog Scale	ITT Population with Observed Data Only
Figure 14.2.7	Ocular Discomfort Scale (Ora Calibra Scale)	ITT Population with Observed Data Only
Figure 14.2.8	Ocular Discomfort & 4-Symptom Questionnaire (Ora Calibra Scale)	ITT Population with Observed Data Only

24. Appendix 1

The multiple imputation methodology will employ a combination of treatment group-based MCMC imputation and placebo-based PMM imputation. Imputation methods will be performed using the SAS® procedure PROC MI. The SAS® code for obtaining randomized treatment group-based MCMC multiple imputation data is:

```
PROC MI DATA = INDATA SEED = 425754 OUT = OUTDATA NIMPUTE = 30
    MINIMUM = 0 MAXIMUM = 4 ROUND = 0.5;
    BY TREATMENT;
    MCMC INITIAL = EM;
    VAR BASE V3 V4 V5 V6;
RUN;
```

where

- INDATA is the name of the input dataset
- OUTDATA is the name of the output dataset
- TREATMENT is the name of the treatment group variable
- [REDACTED]
- V3 – V6 are the CCSS in the study eye at Visit 3 through Visit 6.

After obtaining 30 complete data sets and calculating changes from baseline, the following SAS® code will be used to run the MMRM model on each multiply imputed data set and combine the results from the 30 analyses:

```
PROC MIXED DATA = OUTDATA;
    BY _IMPUTATION_;
    CLASS TREATMENT;
    [REDACTED]
    COVB;
    LSMEANS TREATMENT / CL PDIFF;
    ODS OUTPUT LSMEANS = OUTLS DIFFS = OUTDIFFS;
    RUN;

    PROC SORT DATA=OUTLS; BY TREATMENT _IMPUTATION_; RUN;

    PROC MIANALYZE DATA=OUTLS;
        BY TREATMENT;
        MODELEFFECTS ESTIMATE;
        STDERR STDERR;
    RUN;

    PROC SORT DATA=OUTDIFFS; BY _IMPUTATION_; RUN;

    PROC MIANALYZE DATA=OUTDIFFS;
        MODELEFFECTS ESTIMATE;
        STDERR STDERR;
    RUN;
```

where

- TREATMENT is the name of the treatment group variable
- SITE is the study site id as a random effect

- BASELINE is the baseline CCSS in the study eye
- CFB is the change from baseline in CCSS in the study eye at Day 57
- OUTLS is the name of the output dataset that contains the statistical results for the treatment mean from the MMRM model that is run on each of the twenty imputation datasets
- OUTDIFFS is the name of the output dataset that contains the statistical results for the difference in treatment mean from the MMRM model that is run on each of the twenty imputation datasets

Similar SAS® code will be used to conduct MCMC multiple imputation analysis for the two sample t-test.

Furthermore, the SAS® code for obtaining the placebo-based PMM imputation data is:

```

PROC MI DATA = INDATA SEED = 988416 OUT = MDATA NIMPUTE = 30
  MINIMUM = 0 MAXIMUM = 4 ROUND = 0.5;
  MCMC IMPUTE=MONOTONE;
  VAR BASE V3 V4 V5 V6;
RUN;

PROC MI DATA = MDATA SEED = 253464 OUT = OUTDATA NIMPUTE = 1
  MINIMUM = . 0 0 0 0
  MAXIMUM = . 4 4 4 4
  ROUND = . 0.5 0.5 0.5 0.5;
  CLASS TREATMENT;
  MONOTONE REG(V6 = V5 V4 V3 BASE / DETAILS);
  MONOTONE REG(V5 = V4 V3 BASE / DETAILS);
  MONOTONE REG(V4 = V3 BASE / DETAILS);
  MONOTONE REG(V3 = BASE / DETAILS);
  MNAR MODEL(BASE V3 V4 V5 V6/ MODELOBS=(TREATMENT='Placebo'));
  VAR TREATMENT BASE V3 V4 V5 V6;
RUN;

```

where

- INDATA is the name of the input dataset
- MDATA is the name an intermediary dataset with a monotone missing pattern
- OUTDATA is the name of the output dataset
- TREATMENT is the name of the treatment group variable
- BASE is the baseline CCSS in the study eye
- V3 – V6 is the CCSS in the study eye at Visit 3 through Visit 6

An example of the SAS® code implementation of the MMRM model for the observed data only is as follows:

```
PROC MIXED;
```

Protocol HL036-DED-US-P302 SAP, Version 1.0

```
CLASS PATIENT WEEK TREATMENT;  
MODEL CFB = WEEK BASELINE TREATMENT / SOLUTION COVB;  
[REDACTED]  
LSMEANS TREATMENT / CL PDIFF;  
RUN;
```

25. Appendix 2

Schedule of Visits and Assessments

Procedure	Screening Visit 1 (Day -14 ± 2)	Baseline Visit 2 (Day 1)	Visit 3 (Day 8 ± 1)	Visit 4 (Day 15 ± 2)	Visit 5 (Day 29 ± 2)	Visit 6 (Day 57 ± 3)	Visit 7-9 ⁴
Informed Consent / HIPAA	X						
Medical / Medication History and Demographics	X						
Placebo Run-In Collection		X					
Study Drug Collection			X	X	X	X	
Medical / Medication Update		X	X	X	X	X	X
Pregnancy Test	X ²					X ²	
Ocular Discomfort Scale	X	X	X	X	X	X	
Ocular Discomfort & 4-Symptom Questionnaire	X	X	X	X	X	X	
VAS	X	X	X	X	X	X	
OSDI® Questionnaire	X	X	X	X	X	X	
Visual Acuity (ETDRS)	X	X	X	X	X	X	
Slit Lamp Biomicroscopy	X	X	X	X	X	X	
Conjunctival Redness	X	X	X	X	X	X	
TFBUT	X	X	X	X	X	X	
Fluorescein Stainng	X	X	X	X	X	X	
Lissamine Green Staining	X	X	X	X	X	X	
Schirmer's Test	X	X		X	X	X	
Intraocular Pressure	X					X	
Dilated Fundus Exam	X					X	
Review of Qualification Criteria	X	X					

Placebo Run-In Dispensation and Instillation	X						
Blood Sampling for Immunogenicity		X			X	X	X
Randomization		X					
Study Drug Instillation		X	X				
Drop Comfort Scale		X	X				
Drop Comfort Questionnaire		X	X				
Adverse Event Query	X	X	X	X	X	X	X
Study Drug Dispensation		X ¹	X	X	X		
Exit Subject from Study						X ³	

¹ The Visit 2 study drug kit is re-dispensed at Visit 3 (as each kit includes 2-week supply of study drug).

² To women of child-bearing potential.

³ For subjects with negative immunogenicity results at Visit 6.

⁴ Subjects will be asked to return for Blood Sample for Immunogenicity Testing if they test positive for immunogenicity at Visit 6. Visit 7 will occur approximately 6-12 months after Visit 6. If subject tests positive for immunogenicity at Visit 7, they will be asked to return for Visit 8 approximately 12 months after Visit 7. If subject tests positive for immunogenicity at Visit 8, subject will be asked to return for Visit 9 approximately 12 months after Visit 8.

Certificate Of Completion

Envelope Id: 0FD96C8D49AC44D78A4A23EF3B2091D1 Status: Completed

Subject: Complete with DocuSign: HanAll HL036-DED-US-P302 Statistical Analysis Plan Draft V1.0 23-JAN-20...

Source Envelope:

[figure not shown]
Document Pages: 45 Signatures: 3

Certificate Pages: 5 Initials: 0

AutoNav: Enabled

Enveloped Stamping: Disabled

Time Zone: (UTC-05:00) Eastern Time (US & Canada)

